5 OBJECTIVES AND VARIABLES

The primary objective of the study is *to identify patients with metastatic renal cell carcinoma (mRCC) who obtained a complete response (CR) to treatment with Sunitinib exclusively or with Sunitinib and a local treatment to eliminate residual disease in the opinion of the clinician. Complete response (CR) is defined as the disappearance of all measurable lesions according to the investigator's criterion in at least 2 consecutive CT scans.*

The clinical baseline characteristics of these patients and the tumour will be described in order to look for predictive response factors.

[figure not shown]
The intention is to describe the therapeutic strategy used in patients who obtained the greatest clinical benefit in the cases described once the macroscopic lesions were eradicated in order to draft recommendations to be followed once the registry's statistical analysis is available.

The variables to be analysed for this study will be obtained from the patients' medical records and case report forms according to the protocol. The data will be recorded on the paper CRF designed for this study where the following patient information will be included:

DEMOGRAPHIC AND DISEASE INFORMATION

- 1) Age at the start of treatment for metastatic disease
- 2) Functional status, measured by the ECOG scale (0, 1, 2, 3, 4) and/or by means of the KPS (Karnofsky Performance Status) scale, at the start of treatment (see annex I)
- 3) Motzer and Heng prognostic criteria
- 4) Laboratory data (haemoglobin, leukocytes, corrected calcium, LDH levels, lymphocytes, platelets, neutrophils, lymphocytes)
- 5) Comorbidities
- 6) Date the disease was diagnosed
- 7) Metastasis site(s) and number
- 8) Furhrman grade (I, II, III, IV)

PFIZER CONFIDENTIAL

- 9) Tumour stage (TNM)
- 10) Previous nephrectomy
- 11) Necrosis

TREATMENT

- 1) Start date of treatment with first-line Sunitinib
- 2) Initial dose and treatment regimen
- 3) Type of treatment received (monotherapy or in combination with local treatment) and technique used in the case of local treatment
- 4) Response to treatment.
- 5) Date of completion of the treatment after CR if treatment is interrupted
- 6) Modification of dosage and/or treatment regimen, number of changes in the dose, reason, date and new dose
- 7) Dose interruptions, number of interruptions, reason, date of interruption and restart and new dose

CCI

- 9) Adverse reactions

POST-TREATMENT

- 1) Continuation of treatment in 1st line

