- 2) End date and reason
- 3) Date of progression
- 4) Date of and reason for death
- 5) Post-Sunitinib treatments (another TKI, mTOR, immunotherapy)

The following aspects will be assessed using the variables collected:

- **Time from nephrectomy to the start of systemic treatment:** defined as the time interval from the day of the nephrectomy to the day treatment with Sunitinib started.
- **Time to CR:** defined as the time interval from the day treatment with Sunitinib started until the day the complete response is documented in the first CT scan without lesions.
- **Duration of treatment with Sunitinib once CR is reached:** defined as the time interval from the day on which the complete response is documented until the day that the definitive discontinuation of the treatment is confirmed, either at the patient's own decision or at the doctor's decision.
- **Time to progression (TTP):** defined as the time interval from the day on which the complete response is documented until the first day that objective tumour progression, if any, is observed.
- **Time to change of treatment:** in patients who continue treatment with Sunitinib once the lesions have disappeared, it is defined as the time interval from the day on which the complete response is documented until the first day on which the change of treatment due to unacceptable toxicity is documented, as applicable.
- **Time to death:** defined as the time interval from the day on which the

Pfizer Confidential

complete response is documented to the day on which death from any cause is documented, if it occurs.

- **Duration of complete response (DOR):** defined as the time interval from the date on which the complete response to Sunitinib is identified until the date of the CT scan conforming tumour progression, the change of treatment due to unacceptable toxicity, death from any cause or until the date of the last follow-up at the close of the study. It represents the time that the patient survives without signs of disease.

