7.2.2. Descriptive analysis

The mean value, standard deviation, median, minimum, maximum, interquartile range (RIQ) and 95% confidence interval (CI 95%) of the following variables will be provided:

- Age of the patients at the start of treatment.
- Pre-treatment necrosis percentage

PFIZER CONFIDENTIAL

[figure not shown]

- Laboratory data at the start of treatment:
 - Haemoglobin
 - Leukocytes
 - Corrected calcium
 - LDH levels
 - Lymphocytes
 - Platelets
 - Neutrophil/Lymphocyte rate
- Time elapsed from the nephrectomy to the start of systemic treatment
- Time on treatment until CR is reached
- Duration of CR
- Time on treatment after CR is reached

The frequency distribution of patients will be presented according to:

[figure not shown]
- ECOG:
 - 0
 - 1
 - 2
 - 3
 - 4
- KPS (Karnofsky Performance Status):
 - 0%
 - 10%
 - 20%
 - 30%
 - 40%
 - 50%
 - 60%
 - 70%
 - 80%
 - 90%
 - 100%
- Motzer prognostic criteria:
 - Favourable (0 factors)
 - Intermediate (1-2 factors)
 - Poor (3 or more factors)
- Heng prognostic criteria:
 - Favourable (0 factors)
 - Intermediate (1-2 factors)
 - Poor (3 or more factors)
- Comorbidities:

PFIZER CONFIDENTIAL

- Cerebrovascular disease
 - Liver disorders
 - Renal failure
 - Autoimmune disease
 - Chronic dermatological disease
 - Obesity
 - Bowel disease
- Metastasis site:
 - Lung
 - Liver
 - Brain
 - Pancreas
 - Nodes
 - Other
- Fuhrman grade:
 - I
 - II
 - III
 - IV
- TNM tumour stage
- Histological type:
 - Clear cell
 - Chromophobe
 - Sarcomatoid, percentage
 - <20%
 - 20-30%
 - 31-50%
 - 51-75%
 - >75%
 - Papillary type 1
 - Papillary type 2
 - Mixed
 - Not performed
- Previous nephrectomy:
 - Yes
 - No
- Complications during surgery:
 - Yes
 - No
- Initial dose and treatment regimen:

PFIZER CONFIDENTIAL

- Sunitinib 50 mg 4/2 regimen
- Sunitinib 50 mg 2/1 regimen
- Sunitinib 37.5 mg 4/2 regimen
- Sunitinib 37.5 mg 2/1 regimen
- Sunitinib 25 mg 4/2 regimen
- Sunitinib 25 mg 2/1 regimen

- Type of treatment received:

- Sunitinib monotherapy
- Sunitinib + subsequent local treatment
- Local treatment techniques for residual lesions:
 - Traditional surgery
 - Radiotherapy
 - SBRT

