 - Active participation by the patient in the decision to discontinue the product once CR is reached
 - At the patient's decision
 - At the doctor's decision
 - Other reasons
 - Calculation of total days of treatment interruption

A summary calculation of the dose modifications will be made for the aspects described above. For the calculation of total days of interruption of treatment, descriptive central tendency (mean, median) and dispersion (standard deviation, interquartile range)

PFIZER CONFIDENTIAL

statistics will be presented.

- **Post-treatment.** The absolute and relative frequency of the number of patients who discontinue first-line Sunitinib treatment will be reported definitively after the CR. In the subpopulation of patients who remain on second-line treatment, frequency distribution will be presented for:
 - o Reason for terminating the treatment:
 - Toxicity
 - Progression
 - Death, reason:
 - Progression
 - Toxicity, in this case:
 - ✓ In the investigator's opinion related to Sunitinib
 - ✓ Not related to Sunitinib
 - Another reason
 - o Total number of days of duration of treatment with second-line Sunitinib.
 - o Post-second-line Sunitinib pharmacological treatment group after disease progression after a period of CR:
 - TKI
 - mTOR
 - Immunotherapy

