7.2.4. Efficacy analysis

Depending on the **primary objective of the study**, the complete responses (CR) observed in Spanish daily clinical practice in patients with advanced carcinoma with a renal cell component that have received first-line treatment with Sunitinib will be described. All demographic and clinical characteristics will be summarised descriptively.

More specifically, the following baseline features of both patient and tumour will be described:

- Demographic characteristics (age at the start of treatment of the metastatic disease).
- Comorbidities: presence of cardiovascular, hepatic, renal, autoimmune, chronic dermatological, obesity and/or intestinal disease.
- Tumour data: number and site of metastases, tumour histology, Fuhrman grade and presence of tumour necrosis.
- Previous nephrectomy in the treatment of metastatic renal cancer and time elapsed from nephrectomy to the start of systemic treatment.
- Classification of the risk group according to Motzer and/or Heng criteria.
- Patient's baseline status, including ECOG grade, presence of anaemia, corrected calcium, LDH levels, neutrophil and platelet levels.

Central tendency measures (mean and median) and dispersion measures (standard deviation and interquartile range) will be used for the quantitative variables. Frequency distributions (absolute and relative) will be presented for categorical data. Bivariate comparisons between baseline characteristics and events of interest of a continuous nature will be made by parametric tests (Student's t test, one-way ANOVA) or their non-parametric equivalents (Mann-Whitney, Kruskal-Wallis) depending on the distribution of the variables. In the case of categorical variables, the Chi-squared test or Fisher's exact

PFIZER CONFIDENTIAL

test, as applicable, will be used for the comparison of frequency distribution.

The **secondary outcome measures** pertaining to the follow-up time until the event of interest (complete disease remission, disease progression, change of treatment due to unacceptable toxicity or death from any cause) will be described by estimating survival functions using the Kaplan-Meier method. Specific estimates and 95% confidence intervals will be provided for the median, 25th percentile and 75th percentile of the distributions of each secondary variable. The secondary outcome variables related to follow-up time are:

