- Time on treatment with Sunitinib until complete remission of lesions, calculated as the difference between treatment start date and CR confirmation date (2nd CT scan).
- Duration of complete remission (DOR)
- Progression-free survival (PFS) or time from remission to disease progression, change of treatment due to unacceptable toxicity or death. It will be calculated as the time elapsed from the RC confirmation date (2nd CT scan) until the date of progression/death or change of treatment for unacceptable toxicity, as applicable, or else it will be censored on the date of the last patient follow-up.

Taking into account the asymmetry normally observed in the distribution of survival times and that follow-up periods may be uneven (different study entry date), the Kaplan-Meier method will be used to estimate the median time to CR together with its 95% confidence interval. The median will indicate when complete remission of the disease occurred in 50% of patients.

In order to find associations between time to CR and the baseline features of both patient and tumour, a log-rank test will be used for comparison between groups and the determination of the statistical significance of the correlation between each of the baseline variables and the time to complete remission of disease. The following baseline characteristics are considered:

[figure not shown]
- Demographic characteristics
- Comorbidities
- Tumour data
- Prior nephrectomy in the treatment of metastatic renal cancer
- Classification of the risk group according to Motzer and/or Heng criteria.
- Patient's baseline status, including ECOG grade, presence of anaemia, corrected calcium, LDH levels, neutrophil and platelet levels.

This analysis will establish which baseline characteristics are associated with a shorter complete response time to treatment.

As part of the secondary objectives, the doses and treatment regimens observed in the sample will also be descriptively summarised by means of absolute and relative frequencies. In the case of changes in the treatment dose, the frequency of patients with dose increase, dose reduction and changes in the rest regimen will be specified. Similarly, the most frequent reasons for changes in dosage and/or treatment regimen to RC will be reported.

Frequencies of the type of treatment received will be presented, depending on whether it

Pfizer Confidential

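### The SAP gives time to CR two different end dates, and has no rule for patients still on sunitinib when it summarises treatment time after CR

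*SAP*

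**What the plan says.** **Time to CR.** SAP section 5 runs it from the start of sunitinib "until the day the complete response is documented in the first CT scan without lesions". SAP section 7.2.4 lists time on sunitinib until complete remission among the secondary time-to-event outcomes, "calculated as the difference between treatment start date and CR confirmation date (2nd CT scan", and plans a Kaplan-Meier median with a 95% confidence interval. The median of this time is a named secondary objective in protocol 7.2 and SAP 2.2.

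**Time on sunitinib after CR.** SAP section 5 runs it from documented CR "until the day that the definitive discontinuation of the treatment is confirmed, either at the patient's own decision or at the doctor's decision". The treatment data list in the same section asks for "Date of completion of the treatment after CR if treatment is interrupted". SAP 7.2.2 promises "The mean value, standard deviation, median, minimum, maximum, interquartile range (RIQ) and 95% confidence interval (CI 95%) of the following variables will be provided", and that list includes "Time on treatment after CR is reached". SAP 7.2.4 says the secondary follow-up times "will be described by estimating survival functions using the Kaplan-Meier method" and names three: time to CR, duration of CR (DOR) and PFS from remission. Time on sunitinib after CR is not among them. SAP 5.4 classes it as a covariate. SAP 6 completes partial dates and replaces no other missing value.

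**The concern.** The protocol leaves full variable definitions to the SAP, so no other document settles which CT ends time to CR. Two analysts could each follow the SAP and report different medians for the same secondary objective.

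The registry exists because there is no guidance on continuing or stopping sunitinib once lesions have gone, and the SAP intends to draw recommendations from the data. How long patients stayed on drug after CR is a figure readers will use for that question. The records are reviewed once, so some patients will still be on sunitinib at review. They have no stop date, and the SAP does not say whether to drop them, cut them at last contact or censor them. Patients still on drug tend to be those treated longest, so a raw summary that leaves them out understates the duration.

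**Working it through.** The documents give no figure to reproduce for either outcome. The SAP text can be compared directly; the sizes are illustrations under stated assumptions.

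**Part 1: time to CR.**

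Inputs: cited medians of 10.1 months (Czech registry), 12.6 months (French series, drug alone) and 18.5 months (French series, drug plus local treatment). The scan gap is not fixed for this study. I assume 4 weeks (28 days, 0.92 months), the minimum in the French series, up to 3 months.

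Moving from the first to the second clear CT adds each patient's own gap, so with a constant gap: relative shift of the median = gap / median.

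| Median (months) | Gap 0.92 | Gap 2 | Gap 3 |
|---|---|---|---|
| 10.1 | 9.1% | 19.8% | 29.7% |
| 12.6 | 7.3% | 15.9% | 23.8% |
| 18.5 | 5.0% | 10.8% | 16.2% |

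Effect on tests: a constant gap leaves the ranks unchanged. With gaps uniform from 0.92 to 3 months, 45 patients per group and an assumed hazard ratio of 1.5 (8,000 runs), log-rank z values from the two definitions correlate 0.998. Significance changes in 2.3% of runs (10.1-month median) and 1.8% (12.6-month median).

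**Part 2: time on sunitinib after CR.**

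| Outcome | Raw list, SAP 7.2.2 | Kaplan-Meier, SAP 7.2.4 | Rule for open cases |
|---|---|---|---|
| Time to CR | yes | yes | not needed: every eligible patient has CR |
| DOR | yes | yes | last follow-up (SAP 5) |
| PFS from remission | no | yes | censored at last follow-up (SAP 7.2.4) |
| Time on sunitinib after CR | yes | no | none |

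Only the last row has raw statistics alone and no rule for open cases.

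Illustration inputs: 17% still on drug (17 of 100 CR patients in the Czech registry); CR dates uniform from June 2007 plus 12.6 months to 30 October 2018; cut in January 2019 or on 31 July 2019; scale of the duration distribution solved so that 17% are ongoing at the cut.

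Exponential durations:

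- January cut, true median 16.1 months. Ongoing counted as ended: 13.8, and 13.8/16.1 - 1 = -14%. Ongoing dropped: 13.0, and 13.0/16.1 - 1 = -19%.
- July cut, true median 20.3 months. Counted as ended: 18.0 (-11%). Dropped: 15.9 (-22%).
- In samples of 90 (0.17 x 90, about 15 ongoing), counting ongoing as ended gives a mean raw median of 13.9 against a Kaplan-Meier 16.3 (January), and 18.2 against 20.4 (July). Kaplan-Meier with censoring recovers the true value.
- A different set-up (true median 12 months, uniform censoring, 17% ongoing) gives 10.3 if counted as ended (-14%) and 10.0 if dropped (-17%).

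The exponential shape is itself an assumption. Over Weibull shapes 0.5 to 2, both cuts, 17% ongoing:

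- ongoing dropped: raw median 7% to 40% low;
- ongoing counted as ended: raw median 0% to 14% low.

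The 0% case is the July cut with shape 0.5. Every patient then has at least 9 months of follow-up (30 October 2018 to 31 July 2019), which exceeds the true median, so nobody is cut off before it.

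**The case against.** The strongest case on the other side has four parts.

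- **Rank and weight.** This is a descriptive registry with no hypothesis, and SAP 5.4 makes post-CR treatment time a covariate, not an objective. That stands and limits the weight of part 2. SAP 7.2.2 nevertheless commits to reporting its mean, median and confidence interval.
- **Intended meaning.** SAP 5 defines time to progression, time to change for toxicity and time to death separately. Post-CR treatment time could therefore be meant only for patients who stopped by decision, and leaving out ongoing patients would then be the definition rather than a bias. This is a fair reading, but the SAP does not state it, and nothing in 7.2.2 restricts the summary to that group.
- **Choice of CT.** CR itself requires two consecutive clear CTs, so either date can work if used consistently. That stands: the defect is the conflict, and the choice of date is a preference.
- **Support for other stop reasons.** SAP 7.2.3 lists toxicity, progression and death under "Reason for terminating the treatment", but ties that list to patients on second-line treatment, and the text is garbled. It is weak evidence of what the post-CR definition should cover.

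A reader might also infer that the different starts of DOR and PFS are a further error. The documents do not support that. The protocol starts DOR at the first CT and a separate objective at confirmation of CR, and the SAP labels its PFS start as the second CT. DOR is already in the Kaplan-Meier list, and last follow-up is plainly not one of its events.

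**Conclusion.** Both parts hold and should be corrected; neither is critical.

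Part 1 is a direct conflict in the SAP over a named secondary outcome. It moves the reported median by the scan gap: about 5% to 30% of the cited medians if the gap is 4 weeks to 3 months, which is an assumption. A reader might infer that the log-rank and Cox findings are also at risk. They are not to any material degree.

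Part 2 is a missing rule for a covariate that matters to the registry's purpose. If patients still on drug are dropped, the duration is understated: 7% to 40% for the median in the illustration. If they are counted as ended, the median is 0% to 14% low. A reader might infer that every handling must bias the median downward; the 0% case shows otherwise.

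These sizes rest on 17% still on drug and Weibull shapes 0.5 to 2. The Czech share is a loose anchor: one image sufficed for CR there, and the same account speaks both of 65 patients who stopped without documented relapse and of 30 who stopped after CR. For that reason its split by stop reason cannot be used to size the effect of counting or censoring particular stops.

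**What to change.** 1. Use one CR date for time to CR in SAP 5 and 7.2.4. The first clear CT, with the second as confirmation, matches SAP 5 and the protocol's start of DOR. The second-CT date can be a sensitivity analysis.
2. Move time on sunitinib after CR from the raw list in 7.2.2 to the Kaplan-Meier list in 7.2.4. Start it at the same CR date, censor patients still on sunitinib at last contact, and take any permanent stop as the event. Report cumulative incidence by reason (decision, toxicity, progression, death) beside it.
3. If only patients who stopped by decision are meant, say so and label the raw summary as restricted to them.

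The cost is SAP rewording, one Kaplan-Meier estimate and an optional cumulative-incidence table. No new data are needed: the two SAP definitions and the eligibility rule already call for both scans, SAP 5 collects the end date and reason, and the protocol's variables section collects the date of last contact.
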